Wound Assessment/ Debridement	X	X	X		X		
Tissue /bone ¹ / wound culture samples for qPCR cultures & bioburden analysis		X	X (Subsequent surgery)				

			while Inpatient)				
NPWT/NWPT (i) randomization/dressing application/changes		X	X	X (Weeks 2-4)	X (Weeks 2-4)		NWPT for maximum 4 weeks after baseline(Day0 surgery) if wound is not closed in the hospital
SF-36 Questionnaire	X					X	
Hyperspectral Imaging Analysis	X						To occur prior to surgery
Discharge Instructions			X		X		
Offloading			X	X	X		At hospital discharge & continuing to Week 12
Adverse Events		X	X	X	X	X	
Current/concomitant antibiotics	X	X	X	X	X	X	
Wound imaging/measurement		X	X		X	X	While active study wound is present
Neuropathy Disability Score in Patients with Diabetes	X						

¹ Only if performed as a necessary part of standard of care.

² Subjects who heal before week 12 will exit the study and complete EOS visit.

Biostatistics

Sample Size Justification:

There are no published data with the Cardinal PRO negative pressure wound therapy (NPWT) device with or without irrigation in order to determine an estimate of the sample size for this study. One of the purposes of this project is to obtain data, so we can power a larger multicenter study. Even though the KCI NPWT device with irrigation has been commercially available, there is little data about volume change or wound healing in the population we are studying.

The previous sample size justification was based on a comparison of the proportion of wounds expected to achieve surgical closure. The proportion of subjects with closed wound was 62% using traditional KCI NPWT and 94% using NPWT with periodic irrigations with Prontosan. For the sample size, we estimated 85-90% wound closure with NPWT with irrigation and 60% wound closure with NPWT without irrigation. We assume the NPWT devices (KCI and Cardinal) without irrigation would have similar results.

Equations

The following formula was used to estimate the required sample size, n , for the relative difference in proportions P_1 and P_2 .

$$n = \frac{\left(Z_{\alpha/2} \sqrt{2P(1-P)} + Z_{\beta} \sqrt{P_1(1-P_1) + P_2(1-P_2)} \right)^2}{(P_1 - P_2)^2}$$

where

$$P = \frac{P_1 + P_2}{2}$$

Using the formula above and assuming 90% wound closure with NPWT with irrigation and 60% wound closure with NPWT without irrigation and a type I error of 0.1, the required sample size is about 25. If a Type I error of 0.05 is assumed, then the required sample size is about 31.

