As the relative difference gets smaller, the required sample size increases. The two tables below show estimates for sample size for values of alpha of 5% and 10% for five values of P_2 .

P_1	P_2	rel. difference	$\alpha/2$	β	power	n
0.6	0.9	-0.75	.05	0.200	0.800	25
0.6	0.89	-0.73	.05	0.200	0.800	27
0.6	0.88	-0.70	.05	0.200	0.800	29
0.6	0.86	-0.65	.05	0.200	0.800	35
0.6	0.85	-0.63	.05	0.200	0.800	41

P_1	P_2	rel. difference	$\alpha/2$	β	power	n
0.6	0.9	-0.75	.025	0.200	0.800	31
0.6	0.89	-0.73	.025	0.200	0.800	34
0.6	0.88	-0.70	.025	0.200	0.800	37
0.6	0.86	-0.65	.025	0.200	0.800	45
0.6	0.85	-0.63	.025	0.200	0.800	51

PRELIMINARY DATA: Kim PJ, Attinger CE, Steinberg JS, Evans KK, Powers KA, Hung RW, Smith JR, Rocha ZM, Lavery L. The impact of negative-pressure wound therapy with instillation compared with standard negative-pressure wound therapy: a retrospective, historical, cohort, controlled study. *Plast Reconstr Surg.* 2014 Mar;133(3):709-16.

This study shows that NPWT with two different doses of Prontosan irrigation solution decreases the number of surgeries, length of hospitalization, and increases the proportion of wounds that are closed compared to “traditional NPWT”. We conducted a retrospective study of hospitalized patients with infected lower extremity wounds that received NPWT without irrigation (n=74), NPWT with irrigation with polyhexanide biguanide (PHMB) with a 6 minutes dwell time (n=34), and NPWT with irrigation with polyhexanide biguanide (PHMB) with a 20 minute dwell time (n=34). The proportion of wounds that were surgically closed was significantly higher, and the number of surgeries was significantly less in patients that received NPWT with 6 minutes of irrigation compared to standard NPWT without irrigation. Similar trends were seen with NPWT with 20 minutes of irrigation.

Table 1	NPWT n=74	NPWT 6 minute irrigation n=34	NPWT 20 minute irrigation n=34
Number of Surgeries	3.0 ± 0.9	2.4 ± 0.9 p=0.04	2.6 ± 0.9 p=0.003
Length of Stay (days)	14.9 ± 9.2	11.9 ± 7.8 p=0.10	11.4 ± 5.1 p=0.03
Time to Final Surgical Procedure	9.23 ± 5.2	7.8 ± 5.2 p=0.04	7.5 ± 3.1 p=0.002
Percent Closed	62%	94% p<0.001	80% p=0.08

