Continuous demographic parameters, such as the patient's age at the time of enrollment, will be summarized for the population using descriptive statistics (N, mean, median, standard deviation, minimum and maximum value, and 95% 2-sided confidence limits) and compared between groups using a 2-sample t-test. Categorical demographic parameters, such as gender, were summarized as a proportion of the intent-to-treat (ITT) population and compared using a 2-tailed Fisher's exact test. Co-morbid risk factors will be summarized for the ITT population by treatment assignment and according to the type of variable (categorical, continuous) and compared between groups. Relative risk will be evaluated using a logistic regression model.

For direct comparisons of the NPWT PRO and KCI Ultra systems, a traditional non-inferiority statistical procedure will be performed. It will be assumed that the efficacy of the NPWT PRO device in wound outcomes is not inferior to the KCI device if it performs within $\pm 10\%$ of the performance of the KCI Ultra system.

Microbial Diversity

Results from the qPCR assessment of bio-burden will be analyzed using standard multivariate approaches. Multivariate differences in bacterial composition among groups will be evaluated using distance based redundancy analysis (dbRDA) [128]. For the dbRDA, distances among samples first will be calculated using unweighted UniFrac distances. UniFrac distances are a robust phylogenetic measure that is useful for comparing microbial communities [129]. An ANOVA-like simulation will then be used to test for group differences.

Facilities

The University of Texas Southwestern Medical Center's Musculoskeletal and Vascular Effectiveness Research Collaboration (MAVERIC) group has 1,200 square feet of dedicated research and clinic space. We have office space for four investigators and seven research coordinators and two nurse coordinators. We have arterial Doppler systems, vibration perception threshold testing equipment and computer workstations. Research patients are seen at the NIH sponsored research center at the University of Texas (5 treatment rooms, laboratory) and the Ambulatory Surgery Center at Parkland Hospital (6 treatment rooms).

- *Human Subjects Research:* The proposed involvement of human subjects, characteristics of the subject population, inclusion/exclusion criteria, and recruitment and consent procedures are described in the Experimental Design and Methods section of this proposal.

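### Relative risk is assigned to logistic regression, which yields an odds ratio, with no conversion step; reported as a relative risk for a common outcome, it would exaggerate the effect

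*Combined protocol and SAP*

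**What the plan says.** The sentence is "Relative risk will be evaluated using a logistic regression model". It closes a paragraph on demographic and co-morbidity summaries in the Biostatistics section (Survival Analyses Models). It names no outcome, event direction, treatment comparison or covariates. The plan nowhere mentions an odds ratio, log-binomial or Poisson regression, or standardisation.

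The Cox paragraph just before it likens its own output to that of logistic regression: maximum likelihood estimates of the model parameters, with p-values and confidence intervals. For a logistic model those parameters are log odds ratios.

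The binary outcome for which the plan gives rates is closure. Under Sample Size Justification, "we estimated 85-90% wound closure with NPWT with irrigation and 60% wound closure with NPWT without irrigation". The retrospective cohort used as preliminary data is summarised there as "The proportion of subjects with closed wound was 62% using traditional KCI NPWT and 94% using NPWT with periodic irrigations with Prontosan", and its table adds the longer dwell time: "Percent Closed 62% 94% p<0.001 80% p=0.08". For the two devices without irrigation, "We assume the NPWT devices (KCI and Cardinal) without irrigation would have similar results".

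**The concern.** An odds ratio approximates a relative risk only when the event is uncommon in both arms. Closure is expected in 60% to 90% of wounds. An analyst who fits the named model, exponentiates the treatment coefficient and gives it the plan's label would report an odds ratio as a relative risk. With an event this common, the odds ratio lies further from 1 than the risk ratio whenever the arms differ, so a reader would take the effect to be larger than it is. At stake are the size and label of a reported estimate.

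**Working it through.** **The plan's own figure first.** The documents state no odds ratio or relative risk, so the check is that the closure rates are read as the plan uses them. The printed formula is applied with P1 = 0.60, P2 = 0.90, P = 0.75 and 80% power.

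- Type I error 0.10: [1.645 × √(2 × 0.75 × 0.25) + 0.842 × √(0.24 + 0.09)]² / 0.30² = 24.7, so 25 per group. The plan says 25.
- Type I error 0.05: the same with 1.960 gives 31.5. The plan says "If a Type I error of 0.05 is assumed, then the required sample size is about 31"; rounding up would give 32.

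All ten rows of the two sample-size tables reproduce within 2 patients. The rates are therefore read correctly.

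**Formulas.** With p1 the proportion without irrigation and p2 with irrigation, RR = p2/p1 and OR = [p2/(1−p2)] / [p1/(1−p1)]. The gap is the ratio of the two, expressed as a number above 1.

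For 60% against 90%: OR = (0.90/0.10)/(0.60/0.40) = 9.0/1.5 = 6.0; RR = 0.90/0.60 = 1.50; gap = 6.0/1.50 = 4.0.

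| Event and rates (p1 against p2) | Source | OR | RR | Gap |
|---|---|---|---|---|
| Closure, 60% against 90% | Sample size | 6.0 | 1.50 | 4.0-fold |
| Closure, 60% against 85% | Sample size | 3.78 | 1.42 | 2.7-fold |
| Closure, 62% against 94% | Cohort, 6-minute dwell | 9.6 | 1.52 | 6.3-fold |
| Closure, 62% against 80% | Cohort, 20-minute dwell | 2.45 | 1.29 | 1.9-fold |
| Closure, 60% against 70% | Assumed smaller effect | 1.56 | 1.17 | 1.3-fold |
| Closure, 60% against 65% | Assumed smaller effect | 1.24 | 1.08 | 1.1-fold |
| Non-closure, 40% against 10% | Complement of sample size | 0.167 | 0.25 | 1.5-fold |
| Complication, 10% against 5% | Assumed; no rate in the plan | 0.47 | 0.50 | about 1.06-fold |
| Closure, equal rates | Device contrast as assumed | 1 | 1 | none |

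**At the trial's size.** Ninety patients randomised 1:1:1 give 30 per arm. The expected closures at 60% and 90% are 18/30 and 27/30. On those counts:

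- exponentiated logistic coefficient: 6.0 (95% CI 1.5 to 24.3);
- modified Poisson regression with robust variance: RR 1.50 (95% CI 1.09 to 2.06);
- marginal standardisation of the same logistic fit: RR = 0.90/0.60 = 1.50.

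The logistic model can therefore supply a valid relative risk, but only through a step that the plan does not contain.

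**The case against.** A reader might infer that this trial's relative risk will be overstated several-fold. The documents do not support that, for four reasons.

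- **The plan does not say that the raw odds ratio will be printed as the relative risk.** A careful analyst could standardise the logistic fit and obtain 1.50. This stands, and it makes the exaggeration conditional. It does not remove the gap: no such step is given, and the only output described for logistic regression is parameter estimates with their intervals.
- **Closure is not assigned to this model.** Time to closure goes to Kaplan-Meier and log-rank, the primary endpoint under Objective 1 is reduction in wound volume, and the closure rates belong to what the plan calls its previous sample size justification. This stands too. However, Objective 1B hypothesises a higher proportion of healed wounds, so closure is a natural candidate, and leaving the outcome unnamed is itself a gap.
- **The multiple depends on which event is modelled.** The relative-difference column of the sample-size tables is on the non-closure scale: (0.10 − 0.40)/0.40 = −0.75. The multivariable Cox modelling is likewise aimed at non-healing and complications. On the non-closure scale the gap at the planning rates is about 1.5-fold. This stands.
- **Two further inferences lack support.** No complication rate is given, so nothing shows that effects on complications would look much larger. The plan says that its data will help power a larger multicentre study, but not that this ratio would be the input; its own sample size used arm-level proportions.

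**Conclusion.** The point holds as a conditional one. The plan pairs relative risk with a model whose coefficient gives an odds ratio and supplies no conversion. If that odds ratio is reported as a relative risk, the exaggeration is 2.7- to 4.0-fold for closure in the irrigation contrast at the planning rates. It is 1.5-fold for non-closure at 40% against 10%, and 1.1- to 1.3-fold if closure differs by only 5 to 10 percentage points. For a complication at an assumed 10% against 5% it is about 1.06-fold, and for the device contrast it is nil if closure rates are equal, as the plan assumes.

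The several-fold figure therefore needs three things together: the odds ratio carrying the relative-risk label, closure as the event, and an effect as large as the one planned for. The test of no effect is the same on either scale, and the Kaplan-Meier and log-rank analysis called primary is untouched. This is a fault in how a supporting estimate is specified and labelled. It should be corrected, but it does not threaten the main comparison.

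**What to change.** Replace the sentence with one along these lines:

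> For each binary outcome [list, stating the event counted and the time point], relative risks and risk differences with 95% confidence intervals will be estimated for each planned comparison by modified Poisson regression with robust variance, with covariates [list]. Any exponentiated logistic coefficient will be labelled an odds ratio and shown with the proportion in each arm.

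Log-binomial regression or marginal standardisation of the logistic model would serve equally well; the plan should choose one. Changing the model without naming the outcome and event direction would leave half the gap open, because the size of the discrepancy turns on both. The cost is a sentence or two of analysis text and a different model command, with no extra data or visits.

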the classical signs of infection in diabetes are blunted because of leukocyte dysfunction, peripheral neuropathy, and peripheral arterial disease (PAD) [80]. Evolving technology such as quantitative PCR, provides an opportunity to accurately identify and quantify bacterial pathogens and perhaps even to redefine “infection” based on objective measurements. Infections $>10^5$ organisms per gram of tissue are associated with infection and delayed wound healing in chronic wounds [81, 82]. In a study by Xu et al., the rate of healing had a strong inverse relationship with log colony forming units (CFUs). For every log order of CFUs there was a 44% delay in wound healing [83].

To date, there are no head-to-head comparisons of fully powered, electrical NPWT devices to determine either superiority or noninferiority. KCI is the market leader in this category and therefore a study to determine whether Cardinal’s PRO NPWT device is noninferiority is necessary. In addition, there are no studies that report a comparison of the economic parameters – both direct and indirect costs – between two NPWT devices.

NPWT with Irrigation

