This study is designed to assess the efficacy and economics of two NPWT branded devices of wound healing outcomes. It is also designed to assess the effectiveness of negative pressure and negative pressure with continuous irrigation on multiple parameters of wound healing. It is a single-center, open-label, active controlled, parallel-group trial that aims to determine the efficacy of Quantum with simultaneous irrigation in the treatment of diabetic foot ulcers. Specifically, eligible participants will be randomized to receive either PRO negative press therapy with simultaneous irrigation; or PRO negative pressure therapy without irrigation; or KCI Ultra negative pressure therapy. Primary outcomes will include rates of wound healing, time to closure by secondary intention, and recurrence rate.

Study Objectives and Endpoints

Objective 1

- A) To compare clinical outcomes in Wounds treated with Negative Pressure Wound therapy with and without Simultaneous Irrigation.**

H1: The wound healing outcomes of patients treated with NPWT Pro will be non-inferior to the wound healing outcomes of patients treated with NPWT-KCI Ultra

Primary Endpoint:

- Comparison of reduction in wound volume between wounds treated with NPWT PRO and NPWT-KCI Ultra

Secondary Endpoints:

- Comparison of rate of wound healing in wounds treated with NPWT PRO and NPWT-KCI Ultra.

- Comparison of the following variables between the groups: granulation tissue integrity including hypergranulation state, time to close, flap/graft take, dehiscence, and reoccurrence.

B) To compare clinical outcomes in Wounds treated with NPWT PRO with and without Simultaneous Irrigation.

H1: Patients treated with NPWT with irrigation will have higher proportions of wounds that heal and faster wound healing trajectories compare to patients treated with NPWT without irrigation.

H2: Patients treated with Negative Pressure Wound therapy with Irrigation will have fewer wound complications such as infections, amputations, and foot-related hospital admissions.

Primary Endpoints:

- Primary Endpoint: Comparison of reduction in wound volume between wounds treated with NPWT PRO and NPWT PRO with simultaneous irrigation

Secondary Endpoints:

- Comparison of rate of wound healing in wounds treated with NPWT and NPWT with simultaneous irrigation

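### The PRO-versus-KCI non-inferiority rule is a two-sided ±10% band with no confidence limit or alpha, and it is not tied to the wound-volume primary endpoint

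*Combined protocol and SAP*

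**What the plan says.** The first hypothesis of Objective 1A (Study Objectives and Endpoints) is one-directional: "The wound healing outcomes of patients treated with NPWT Pro will be non-inferior to the wound healing outcomes of patients treated with NPWT-KCI Ultra". The primary endpoint under it is "Comparison of reduction in wound volume between wounds treated with NPWT PRO and NPWT-KCI Ultra".

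The whole analysis plan for this comparison is two sentences at the end of Biostatistics, Survival Analyses Models. The first says that "a traditional non-inferiority statistical procedure will be performed". The second gives the criterion as "the efficacy of the NPWT PRO device in wound outcomes is not inferior to the KCI device if it performs within", with the band then set at ±10% relative to KCI's result or in points, which the sentence does not spell out. The outcome is described only as wound outcomes. No confidence limit, alpha or sidedness is given.

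The same section names Kaplan-Meier estimates with a log-rank test between two treatment groups as the primary method. Sample Size Justification covers only irrigation against no irrigation on closure proportions, and assumes that the two devices without irrigation perform alike. It adds: "There are no published data with the Cardinal PRO negative pressure wound therapy (NPWT) device with or without irrigation", and "One of the purposes of this project is to obtain data, so we can power a larger multicenter study".

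**The concern.** A non-inferiority claim needs a rule fixed in advance that compares a confidence bound with a margin in one direction. The stated criterion supplies the number 10% and little else. It can be read in three ways:

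1. The observed PRO result must fall inside the band.
2. The whole confidence interval must fall inside the band (equivalence).
3. The lower confidence limit must lie above the negative margin (ordinary non-inferiority).

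These readings can give opposite conclusions from the same data. The trial is open-label, and nothing in the plan fixes the choice before results are seen. The ± sign also means that, taken literally, a PRO device that is clearly better than KCI fails. The log-rank test named as the primary method cannot fill the gap: it tests for a difference, and a non-significant difference does not show non-inferiority.

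**Working it through.** **Inputs from the documents.** 90 patients (Subjects and Recruitment) randomised 1:1:1 (Randomization) gives 90/3 = 30 per arm. Closure without irrigation is 60%, and the two devices are assumed similar (Sample Size Justification). The margin is 10%. Its scale is not stated outright. It is taken as 10 points absolute, or as 10% of KCI's result (0.10 × 60 = 6 points, so PRO at 54%).

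**Assumptions.** One-sided alpha 0.025, with 0.05 as the alternative. Closure serves as illustration because the documents give no wound-volume data.

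**The plan's own figure.** For 60% versus 90%, P = 0.75 and 80% power, the printed formula gives:
- alpha 0.10: (1.645 × 0.6124 + 0.8416 × 0.5745)² / 0.09 = 24.7 (plan: about 25)
- alpha 0.05: (1.960 × 0.6124 + 0.8416 × 0.5745)² / 0.09 = 31.5 (plan: about 31)

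So the plan's sizing reproduces, but it is for irrigation superiority. There is no figure for non-inferiority to reproduce.

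**Reading 1: observed result inside the band.** Binomial probabilities are summed over all outcomes with 30 per arm and true KCI closure 60%. Ranges run from boundary excluded to boundary included.

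| True PRO closure | Passes ±10 points | Passes ±10% of observed KCI |
|---|---|---|
| 40% (20 points worse) | 16–25% | 9–10% |
| 50% (at the absolute margin) | 37–50% | 23–24% |
| 54% (at the relative margin) | 44–59% | 29–30% |
| 60% (identical) | 49–64% | 33–35% |
| 80% (20 points better) | 15–23% | 12–13% |

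A PRO 20 points better meets the absolute band at most 23% of the time, solely because of the upper limit.

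**Reading 2: interval inside both limits.** SE = √(2 × 0.6 × 0.4 / 30) = 0.1265. The 95% half-width is 1.96 × 0.1265 = 0.248, about 25 points. An interval roughly 50 points wide does not fit inside a band 20 points wide, so power is essentially zero.

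**Reading 3: lower limit above the negative margin.** Power with identical devices = Φ(margin/SE − z).
- 10 points, one-sided 0.025: Φ(0.791 − 1.960) = 12.1%. Exact enumeration gives 12.3%, with error at the margin 2.6%.
- 6 points, one-sided 0.025: Φ(0.474 − 1.960) = 6.9%. Exact 7.5%, error at the margin 2.9%. Testing PRO − 0.9 × KCI against zero instead gives 7.9%.
- One-sided 0.05, exact: 18.9% (10 points) and 12.3% (6 points).

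**One data set, two answers.** With KCI 18/30 and PRO 17/30 the difference is −3.3 points and the SE 12.7 points, so the 95% CI runs from −28 to +22. Reading 1 with a 10-point band declares PRO non-inferior. Reading 3 does not.

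**Wound volume.** SE = SD × √(2/30), which is 5.16, 7.75 or 10.33 points for assumed SDs of 20, 30 or 40 percentage points. Noncentral-t power (58 df, one-sided 0.025, identical devices) is 48%, 25% and 16% for a 10-point margin, and 21%, 12% and 8% for a 6-point margin. The SDs are assumptions, and the 6-point margin assumes a KCI mean reduction of 60%.

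**The case against.** The strongest defence is that promising a traditional procedure already implies a confidence interval, which makes the observed-result reading strained. That has force. A reader might infer that the sponsor will compare raw rates with the band, but the documents do not establish it, and the pass rates under Reading 1 apply only if the rule is used that way. What remains is that the next sentence, the only one with a criterion, mentions no interval and is two-sided. The plan also cannot borrow an alpha from elsewhere, since Sample Size Justification uses both 0.05 and 0.10 for a different comparison.

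A second defence is that ±10% of KCI's performance is, on plain grammar, relative. That is the more natural reading, and both scales are shown above for that reason. It does not rescue the rule, because confidence is lower on that scale, not higher.

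A third is that gathering data for a larger trial is a stated purpose. This explains the missing sizing. It does not replace a decision rule for a formal hypothesis, and the background presents this comparison as needed: "KCI is the market leader in this category and therefore a study to determine whether" PRO is non-inferior is called necessary.

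The 17-versus-18 example might also suggest that no PRO result can satisfy both Reading 1 and Reading 3. That is not general. KCI 23/30 with PRO 26/30 passes both at 10 points (boundary counted): the difference is 10.0 points and the 95% lower limit about −9.4.

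**Conclusion.** The point holds as a defect in the decision rule. The stated criterion lacks a confidence limit and an alpha, runs in two directions against a one-directional hypothesis, and is detached from the Objective 1A endpoint. Depending on the reading, it gives poor error control (about 37–50% passes at a 10-point margin, about 30% at a relative one), essentially no power, or controlled error with low power (about 12% or 7.5–8% at one-sided 0.025; about 19% or 12% at 0.05). All of these are for closure at 60% with 30 per arm and no dropout.

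Two stronger conclusions are tempting and are not supported. One is that the trial has 12% power for its primary endpoint. That figure is for closure, on an absolute margin, at an assumed alpha. For wound volume the documents give no SD, and the assumed inputs above span 8–48%. The other is that low power is itself an error that calls for more patients. The plan claims no power for this comparison and says it is collecting data for a larger study, so low precision needs to be disclosed, not corrected.

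**What to change.** Replace the criterion sentence in Survival Analyses Models with wording such as:

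*PRO is non-inferior to KCI if the lower limit of the two-sided 95% CI for the comparison of percent wound-volume reduction (Objective 1A primary endpoint) lies above the margin: PRO minus 0.9 × KCI above zero if the 10% is relative to KCI, or PRO minus KCI above −10 percentage points if it is absolute, the scale being fixed before analysis. There is no upper limit. Otherwise non-inferiority is reported as not shown (inconclusive).*

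Add that this test, not the log-rank test, decides Objective 1A. Add also that the comparison is expected to be imprecise at 30 per arm, with a 95% CI half-width for closure of about 25 points.

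The cost is analysis-plan wording and a sponsor decision on the margin scale. Writing percent reduction also settles a choice that Objective 1A leaves open. The non-inferiority aim will read less favourably, since an inconclusive result becomes likely and must be reported as such. The rule itself needs no extra patients or procedures. The time point at which volume is measured (Therapy Administration and Schedule of Events) is a separate matter to reconcile and does not hold up this change.
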